Based on available literature and our pilot data (shown below), **we hypothesize that insulin resistance (IR) and decreased cardiac fitness are central to the NAFLD in adolescents, and the degree of steatosis is negatively correlated with lower fitness and higher IR. Thus, exercise-driven improvements in IHTG levels will be positively associated with the increase in fitness and the decrease in IR levels in adolescents with NAFLD.** We will test our hypotheses through the following specific aims:

Aim 1: Assess the change in IHTG, and CVD and IR markers in subjects with NAFLD after 4 weeks of HIIT, compared to a sex-matched control group also with NAFLD with no training.

1A. Quantitate the change in IHTG. Hypothesis: IHTG will decrease after HIIT, and the change will be greater than that seen in controls.

1B. Measure the changes in fitness and markers of CVD. Hypothesis: HIIT will significantly increase fitness, decrease heart rate variability and blood pressure, and improve atherogenic lipid profile. The changes will be greater than that seen in controls. Changes in fitness and IHTG will correlate.

1C. Estimate changes on IR. Hypothesis: HIIT will decrease IR especially in those with higher baseline IR, and the changes will be greater than that seen in controls. Changes in IR will correlate with changes in fitness and IHTG.

Aim 2: Determine the post-intervention effects of HIIT on IHTG, and CVD and IR markers 3 months after completion of the HIIT in adolescents with baseline NAFLD.

2A. Quantitate the change in IHTG percent. Hypothesis: HIIT will have a sustained positive effect on IHTG, and that IHTG 3-months post-HIIT will be significantly lower compared to baseline level.

2B. Estimate changes on IR and other CVD markers. Hypothesis: HIIT will have a sustained positive effect on IR, and that IR 3-months post-HIIT will be significantly lower compared to baseline level.

Pediatric NAFLD has serious cardio-metabolic health outcomes. Findings of this study will inform clinical providers in the use of HIIT as a modality to treat adolescent NAFLD and associated morbidities, and produce preliminary data for mechanistic studies to probe pathways implicated in the pathogenesis of NAFLD.

Preliminary Results

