Participants can bring a friend or family member to workout with them if they would like. A separate release will be signed by the friend or family member in order to workout at the ACNC fitness facility.

5-Week/Post-Intervention: All Subjects

Study Visit 3 – This visit may last up to 3 hours and include: measurement of body mass and height, FMD, pregnancy screening (if female), DXA, and fitness test as described above. Participants who are in the control group will complete this visit 5 weeks \pm 1.5 week after study visit 2. Participants will be reimbursed for their time with \$25 at the end of the visit.

Study Visit 4 – This visit may last up to 4 hours and include: measurement of body mass and height, vital signs, OGTT, FibroScan, urine collection, and dietary questionnaire as described above. Participants will be reimbursed for their time with \$50 at the end of the visit.

3-Month Follow-up: Exercise Group Only

Study Visit 5 – Participants from the exercise group will be asked to attend a follow-up visit 3 months \pm 2 week after last HIIT session. This visit may last up to 4 hours and include: measurement of body mass and height, hip and waist circumference, vital signs, pregnancy screening (if female), DXA, FibroScan, FMD, OGTT, urine collection, and dietary questionnaire as described above. FMD, pregnancy screening (if female) and DXA will only be completed in the instance that this visit takes place at ACNC. Participants will be reimbursed for their time with \$50 at the end of the visit.

Magnetic Resonance Imaging (MRI)

In addition to the study procedures described above, all participants will complete a MRI scan before the baseline/pre-intervention fitness test, and another MRI scan before the 5-week/post-intervention OGTT. Furthermore, participants in the exercise group will complete an additional MRI scan before the 3-month follow-up OGTT. The MRI scans will be done at the Arkansas Children's Hospital Radiology Department for the determination of hepatic fat content via magnetic resonance imaging. Each visit for completion of a MRI scan will last up to 1.5 hours. Participants will be reimbursed for their time with \$50 after each visit.

Physical Activity Assessment

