Samples will be stored in freezers in the Arkansas Children's Nutrition Center and/or Arkansas Children's Research Institute. The freezers are constantly monitored to ensure that the proper temperature is maintained. Samples will be identified using the subject's unique study acronym along with the date of sample collection and type of sample (e.g. EDTA plasma, serum). Remaining samples may be stored indefinitely or until used up for future analyses. If consented, samples may be used in future studies related liver and/or metabolic health. Participants and/or parents may contact the study's principal investigator, if they choose to withdraw consent to use samples and/or information in future research. In this case, a written letter addressed to the principal investigator expressing their desire to withdraw their consent would be required. If the information and/or samples have been shared or if publication of results has occurred, then we may not be able to remove information and/or samples.

Data Analysis

Exploratory data analysis will be conducted prior to formal statistical analysis. We will examine the distributions of all key variables to check for data errors and ensure that modeling assumptions are not violated. Numerical summaries including means, standard deviations, medians and histogram graphical techniques will be used for continuous variables and frequencies will be computed for categorical variables. For both aims, the primary outcome is IHTG level measured by both FibroScan and MRI, and secondary outcomes are fitness level, and various cardiometabolic disease markers (i.e.; insulin, glucose, adiponectin, etc.). The immediate (Aim 1) and sustained (Aim 2) effect of HIIT will be measured by comparing the changes in outcomes between groups using a linear mixed-effect framework with a subject-level random intercept. Changes in the outcomes are defined as difference between follow up visits (5-week and 3-month) versus the baseline. The independent variables will be group (intervention vs control), visit time (baseline, 5-week, 3-month) and their interaction term. This model specification can test the effect of intervention as well as difference between visits, while correctly account for the within-subject correlation due to repeated visits. Post-hoc contrasts of visit time between 5-week and baseline will be used to test the hypotheses under Aim 1, while contrasts between 3-month and 5-week will be used to test the hypotheses under Aim 2.

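### A lone random intercept imposes one change variance on every visit pair and both arms, so the Aim 1 and Aim 2 standard errors can be wrong in either direction.

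*Combined protocol and SAP*

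**What the plan says.** The Data Analysis section sets out a "linear mixed-effect framework with a subject-level random intercept". Its fixed effects are "group (intervention vs control), visit time (baseline, 5-week, 3-month) and their interaction term". It states that the specification will "correctly account for the within-subject correlation due to repeated visits".

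For Aim 1 it uses "Post-hoc contrasts of visit time between 5-week and baseline". For Aim 2, "contrasts between 3-month and 5-week will be used to test the hypotheses under Aim 2". The Aim 2A hypothesis under Objective/Specific Aims is a different comparison: "IHTG 3-months post-HIIT will be significantly lower compared to baseline level".

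In Study Design and Procedures, the last visit is headed "3-Month Follow-up: Exercise Group Only" and falls 3 months after the final training session. Controls therefore contribute two visits and exercise participants three.

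No other covariance structure, arm-specific variance, robust standard error, small-sample degrees of freedom or fallback is named. The one safeguard is a general look at distributions to "ensure that modeling assumptions are not violated".

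**The concern.** With only a random intercept, any two visits on the same person share the same correlation, and every visit has the same variance. The variance of a change is then one number for all visit pairs and both arms. It is estimated mostly from the exercise arm, including its 3-month data, and is then used for the 5-week comparison with 8 controls.

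The gaps between visits differ, and the last one follows the end of supervised training. Equal correlation is therefore doubtful, and nothing in the documents supports it. If it fails, at least one planned contrast gets the wrong standard error. Aim 1 would lose power or exceed its nominal error rate, and Aim 2 likewise.

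**Working it through.** **Inputs from the documents (Data Analysis).** 38 exercise and 8 control completers; SD 5.4 before and after training; expected fall 11.5 − 9.2 = 2.3 points.

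**Assumptions.** SD 5.4 at 3 months too, complete data, two-sided alpha 0.05, visit levels (not change scores) as the outcome, and all within-subject correlations. Correlations are ordered baseline–5-week / baseline–3-month / 5-week–3-month.

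**The plan's own figure.** 2.3/5.4 = 0.426, the stated 0.43. A two-sided paired t-test at 0.426 needs 46 people for 80% power; 46 × 5/6 = 38.3, giving 38 + 8. So 46 is reproduced as a total, although the plan presents 38 as the exercise-arm requirement. The calculation uses the SD at a visit. It states no change SD and no correlation, so it cannot support equal correlation.

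**Step 1: what the model forces.** Var(Y_t − Y_s) = 2σ_e² for every visit pair and both arms. Residual degrees of freedom: exercise (38 − 1)(3 − 1) = 74; control (8 − 1)(2 − 1) = 7; total 81. With equal SDs the fitted value is, on average,

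σ_e² = 5.4² × [74(1 − mean of the three exercise correlations) + 7(1 − control correlation)]/81.

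The true change variance for a visit pair is 2 × 5.4² × (1 − r), so with arms alike the ratio of model to true standard error is √[(σ_e²/5.4²)/(1 − r)].

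**Step 2: both 3-month correlations lower, arms alike.**

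- 0.85/0.75/0.75: (74 × 0.2167 + 7 × 0.15)/81 = 0.2109. Aim 1: √(0.2109/0.15) = 1.19. Both 3-month contrasts: √(0.2109/0.25) = 0.92.
- 0.90/0.75/0.80: (74 × 0.1833 + 7 × 0.10)/81 = 0.1761. Aim 1: 1.33. 3-month versus 5-week: √(0.1761/0.20) = 0.94. 3-month versus baseline: √(0.1761/0.25) = 0.84.
- 0.90/0.60/0.65: (74 × 0.2833 + 7 × 0.10)/81 = 0.2675. Aim 1: 1.64. 3-month versus 5-week: √(0.2675/0.35) = 0.87. 3-month versus baseline: √(0.2675/0.40) = 0.82.

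Simulation agrees. The average simulated Aim 1 standard error is 17% to 18% too wide in the first case, slightly below the formula because an estimated standard error averages a little less than the root of its expected square.

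| Correlations | Aim 1 power for 2.3 points: random intercept / t-test on 5-week changes | Type I error, 3-month vs 5-week | Type I error, 3-month vs baseline |
|---|---|---|---|
| 0.85/0.75/0.75 | 36% / 50% | 6.9% | 7.1% |
| 0.90/0.75/0.80 | 43% / 67% | 6.6% | 10.0% |
| 0.90/0.60/0.65 | 23% / 67% | 8.9% | 11.0% |
| 0.80/0.80/0.80 | 40.2% / 39.5% | about 5% | about 5% |

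A check of the first power entry: the true Aim 1 standard error is √[2 × 29.16 × 0.15 × (1/38 + 1/8)] = 1.151, and the model's is 1.151 × 1.186 = 1.364. Power is about Φ[(2.3 − 1.99 × 1.364)/1.151] = Φ(−0.36) = 36%.

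The distortion shrinks when the correlations are closer together. At 0.60/0.50/0.50 the ratios are 1.07 for Aim 1 and 0.96 for Aim 2.

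**Step 3: other orderings, arms alike.**

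- 0.75/0.75/0.85: (74 × 0.2167 + 7 × 0.25)/81 = 0.2196. Aim 1: √(0.2196/0.25) = 0.94 (average simulated standard error about 7% too narrow, type I error 6.8%). 3-month versus 5-week: √(0.2196/0.15) = 1.21 (type I error 1.8%). Both signs reverse.
- 0.80/0.60/0.80: 3-month versus 5-week is too wide (1.14), but 3-month versus baseline is too narrow (0.81).

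**Step 4: arms not alike.** Exercise at 0.85/0.75/0.75, controls at 0.75. The model's Aim 1 standard error is √[2 × 29.16 × 0.2196 × (1/38 + 1/8)] = 1.39. The true one is √[29.16 × (2 × 0.15/38 + 2 × 0.25/8)] = 1.43, a ratio of 0.97. The 8 controls dominate the between-arm error, so noisier controls remove or reverse the Aim 1 effect.

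**The case against.** A random intercept is a common choice for three visits and is exact when variances and correlations are equal. The plan also promises to check modelling assumptions. The first point is true but conditional. The second is weak, because looking at each variable's distribution does not reveal unequal correlations between visits, and no alternative is named if a check fails.

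A reader might infer a fixed direction from time decay: Aim 1 always too conservative, Aim 2 always too liberal. The documents do not support that. They give no within-subject correlation, no change SD and nothing on variability at 3 months. If participants respond differently to training and the effect persists, as Aim 2A hypothesises, 5-week–3-month could be the highest correlation, and step 3 shows the signs then reverse. Nor is a lower baseline–3-month correlation sufficient. The 3-month-versus-5-week contrast is too liberal only if that pair's own correlation is low enough relative to the others.

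The strongest objection concerns the remedy. A visit covariance shared by both arms still gives the 8 controls the exercise arm's variance. With exercise at 0.85/0.75/0.75 and controls at 0.75, a pooled t-test on 5-week changes has type I error of about 9.5%, against 5.6% for the random intercept. This stands, and the fix has to address it.

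**Conclusion.** The assurance that the model handles the correlation correctly is not justified as written. It needs equal variances and equal correlations across three unequally spaced visits, and a change variance common to both arms. The documents support neither. That 74 of 81 residual degrees of freedom come from the exercise arm is arithmetic and rests only on the planned completer numbers.

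The direction and size of the error rest on assumed correlations, SD 5.4 at every visit and complete data. They should be reported as a range and not as a prediction. The 22-to-23% versus 66-to-67% power contrast in particular needs correlation to fall from 0.90 to about 0.60, for which the documents offer no evidence.

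In every ordering examined with the arms alike, freeing the covariance by visit brings Aim 1 type I error back to about 5%, at almost no cost when correlations are in fact equal. The change is worth making before the data are analysed. It is a should-do, not a fatal flaw.

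**What to change.** In Data Analysis, replace the random intercept with an unstructured covariance over the three visits, fitted by REML with Kenward-Roger degrees of freedom. This has six covariance parameters instead of two. Name the fallback in advance: if the model does not converge, analyse Aim 1 on 5-week changes and Aim 2 on paired changes within the exercise arm.

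Add an Aim 1 sensitivity analysis that lets the arms have different variances, for example a Welch comparison of 5-week changes. State whether the Aim 2 test is against 5 weeks or against baseline, since Data Analysis and the specific aims differ and the two standard errors can be wrong by different amounts.

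The cost is SAP wording and a few degrees of freedom. If equal correlation holds, the loss is about half a point to one point of Aim 1 power (40.2% versus 39.5% at 0.80). That figure comes from the simple change-score t-test, not from the Kenward-Roger model. Aim 1 type I error may rise if the controls' changes are much more variable than the exercise arm's, which is what the sensitivity analysis is there to show.

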- **Randomization:** Participants will be randomized to the control or exercise group. We will employ a randomized block design with sex as the blocking factor. Participants who are randomized to the control group will not undergo any exercise training. If randomized to the exercise group, participants will be offered to tour the exercise facility for familiarization with location and personnel.

Participants will be compensated with \$25 at the end of the visit. A FitBit activity tracker will be provided for those who complete the study visit to account for differences in activity level at baseline and throughout the study.

Exercise Intervention (High-Intensity Interval Training (HIIT)): Exercise Group Only

HIIT Intervention – Exercise sessions will take place in the ACNC fitness facility. The session will begin with a 5-10 minute low-intensity warm-up, followed by ten 1-minute intervals using exercise equipment (such as elliptical machine and/or bike and/or treadmill) at a work rate that elicits 80-90% of the maximal heart rate determined during the VO_{2max} test. The participants will have two minutes to recover between each effort and will be encouraged to continue to turn the "pedals" over or walk slowly between high-intensity efforts. To finish the session, the participants will perform a 5-10 minute cool-down at a low intensity. Duration and/or intensity may be adjusted, if needed. Each participant will be asked to attend 3 weekly training sessions for 4 weeks. A minimum compliance rate of 50% will be required to remain in the study (at least 6 training sessions) by the end of the training period (4 weeks). Participants will be encouraged to do home exercises in between training sessions, but these will not be recorded other than via FitBit. All exercise sessions will be primarily directed and monitored by an exercise trainer who staffs the Core. However, an exercise physiologist may also conduct exercise training. The exercise trainer or exercise physiologist will monitor heart rate and OMNI score during sessions. Each HIIT exercise session is expected to last up to 1 hour. Compensation will be provided in increments of \$10, \$20, \$30 and \$40 at the end of the 3rd, 6th, 9th and 12th HIIT exercise sessions, respectively. Therefore, participants who attend all 12 HIIT sessions will receive a total of \$100.

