As an exploratory aim, diagnostic performance of FibroScan for the NAFLD adolescent will be determined by discriminating NAFLD status defined by FibroScan against that by MRI to calculate sensitivity, specificity, positive and negative predictive values. Additional agreement statistics such as concordance correlation coefficient and Bland-Altman plots will be provided for the continuous measurements of IHTG levels measured by both methods.

In our pilot data, the IHTG levels were 11.5 ± 5.4 percent at baseline for NAFLD subjects (N=23). With a pre-defined clinically significant change of 20% relative decrease from baseline, we expect the NAFLD subjects' fat percent will be decreased to an average of 9.2 ± 5.4 percent after HIIT intervention, which is an equivalent effect size of 0.43. In order to detect this effect size at 80% power, we will need 38 NAFLD participants in the intervention group, therefore 8 NAFLD subjects in the control group. Accounting for a 20% dropout rate and false-negative screening from FibroScan, we propose to enroll 58 subjects with NAFLD. Therefore, we need to screen no less than 150 subjects at-risk for NAFLD at baseline, to be able to identify 58 subjects with NAFLD (NAFLD prevalence was 40% in our pilot study, see preliminary data section above).

Ethical Considerations

This study will be conducted in accordance with all applicable government regulations and the University of Arkansas for Medical Sciences research policies and procedures. This protocol and any amendments will be submitted and approved by the UAMS Institutional Review Board (IRB) to conduct the study.

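### The Aim 1 contrast is unbiased but does not condition on baseline IHTG, and its standard error draws on a 3-month visit that only the exercise arm attends

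*Combined protocol and SAP*

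**What the plan says.** Hypothesis 1A (Objective/Specific Aims) is a between-arm claim: "IHTG will decrease after HIIT, and the change will be greater than that seen in controls". The Data Analysis section tests it by "comparing the changes in outcomes between groups using a linear mixed-effect framework with a subject-level random intercept", and adds that "The independent variables will be group (intervention vs control), visit time (baseline, 5-week, 3-month) and their interaction term". The contrast between 5 weeks and baseline serves Aim 1.

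Four other places bear on this:
- Sample size (Data Analysis): "we will need 38 NAFLD participants in the intervention group, therefore 8 NAFLD subjects in the control group".
- Randomization (Study Visit 2): "We will employ a randomized block design with sex as the blocking factor". Baseline liver fat is not balanced by design.
- Magnetic Resonance Imaging: "all participants will complete a MRI scan before the baseline/pre-intervention fitness test". Randomisation is listed after that test, so the baseline scan comes first and adjusting for it is legitimate.
- 3-Month Follow-up: "Participants from the exercise group will be asked to attend a follow-up visit 3 months". Controls have no such visit.

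No section adjusts for baseline IHTG or constrains the arms to a common baseline mean.

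**The concern.** With only 8 controls the arms can start at visibly different liver fat by chance. A comparison of raw changes carries part of that difference into the effect estimate, although a baseline value is on file that could remove most or all of it. At stake are some precision and how readily the single between-arm result can be read if the arms start apart.

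The second issue is the standard error. A random intercept gives every pair of visits the same correlation. The Aim 1 standard error therefore depends on how 3-month values track the earlier ones, in one arm only, although Aim 1 does not concern the 3-month visit.

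**Working it through.** **Inputs from the plan (Data Analysis).** Baseline 11.5, SD 5.4; expected 9.2 after training with SD again 5.4; 38 v 8 completers. Effect 11.5 - 9.2 = 2.3 points; 2.3/5.4 = 0.426, the plan's 0.43. At 5:1, 46 completers split 38.3 : 7.7, and 46/0.8 = 57.5, so 58 enrolled. These reproduce. The 38 is close only to a one-sided within-arm calculation (36 by t test); as a two-sample comparison with SD 5.4, 38 v 8 gives 19% two-sided power.

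**Assumed.** Rho is not in the documents; 0.5 to 0.95 is shown. Tests are two-sided at 5% and data are complete.

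**1. What the model estimates.** With complete data the group-by-5-week term is the raw difference in mean change. A REML fit to simulated data without control 3-month visits gave -3.4591 for both.

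**2. Share of imbalance kept.** SE of the baseline difference D = 5.4 × sqrt(1/38 + 1/8) = 5.4 × 0.389 = 2.10. Given D, the contrast has expectation effect - (1 - rho × SDpost/SDpre) × D, which is effect - (1 - rho) × D when the SDs are equal. The share enters with opposite sign.

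**3. Precision, additive effect.** SE(change) = 5.4 × sqrt(2(1 - rho)) × 0.389. SE(ANCOVA) = 5.4 × sqrt(1 - rho²) × 0.389 × sqrt(1 + 1/42). Variance ratio = (1 + rho)/2 × 43/42, which reaches 1 at rho 0.953. Power for 2.3 points is simulated (40,000 trials per rho, sex also in the ANCOVA).

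| rho | Shift for 1-SE imbalance | SE change | SE ANCOVA | Variance cut | Power: change / model ANCOVA / HC3 ANCOVA (%) |
|---|---|---|---|---|---|
| 0.5 | 1.05 | 2.10 | 1.84 | 23% | 18.6 / 23.1 / 21.3 |
| 0.7 | 0.63 | 1.63 | 1.52 | 13% | 28.1 / 31.6 / 28.9 |
| 0.8 | 0.42 | 1.33 | 1.28 | 8% | 39.5 / 41.9 / 38.0 |
| 0.9 | 0.21 | 0.94 | 0.93 | 3% | 66.9 / 67.9 / 62.3 |
| 0.95 | 0.11 | 0.66 | 0.66 | 0% | 92.5 / 92.5 / 88.7 |

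**4. Proportional effect (treated values × 0.8).** Slope on D is, for change, -[(1 - 0.8 rho) × 8/46 + (1 - rho) × 38/46]. For ANCOVA it is about +0.133 rho, because the pooled slope is rho × (0.8 × 37 + 7)/44 = 0.832 rho and (0.8 - 0.832) × 8/46 + (1 - 0.832) × 38/46 = 0.133. Variance ratios and coverage are from 40,000 trials per rho; power is from a check run of 20,000.

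| rho | Variance ratio ANCOVA/change | Slope: change / ANCOVA | Coverage: change / model ANCOVA / HC3 (%) | Power: change / HC3 (%) |
|---|---|---|---|---|
| 0.5 | 0.75 | -0.52 / +0.07 | 93.7 / 90.8 / 94.5 | 22.6 / 23.0 |
| 0.7 | 0.85 | -0.32 / +0.09 | 93.8 / 91.0 / 94.2 | 31.7 / 30.6 |
| 0.8 | 0.91 | -0.23 / +0.11 | 94.1 / 90.6 / 94.3 | 43.1 / 40.2 |
| 0.9 | 1.00 | -0.13 / +0.12 | 95.0 / 90.1 / 94.2 | 67.3 / 61.2 |
| 0.95 | 1.12 | -0.08 / +0.13 | 96.2 / 88.7 / 94.4 | 89.4 / 83.9 |

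**5. The three-visit standard error.** Write the correlations as r12 (baseline, 5 weeks), r23 (5 weeks, 3 months) and r13 (baseline, 3 months), with equal variances. The residual variance is estimated on 37 × 2 = 74 degrees of freedom from exercise and 7 × 1 = 7 from control, so it is about 5.4² × [74(1 - mean r) + 7(1 - r12)]/81, and SE = sqrt(2 × residual variance) × 0.389. The true SE uses 1 - r12 alone. They agree when mean r = r12, that is, when r23 and r13 average to r12. With r12 = 0.8 the true SE is 1.33:
- 0.8/0.8/0.8: formula 1.33; simulated coverage 95.0%.
- 0.8/0.9/0.7: formula 1.33, although the correlations differ.
- 0.8/0.5/0.4: formula 1.91 (simulated 1.90); coverage 99.6%, power 13.7%.
- 0.8/0.95/0.8: formula 1.17 (simulated 1.16); coverage 91.3%.

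**The case against.** The strongest reply is that nothing here is wrong. The plan defines change and compares it between arms, which is what hypothesis 1A asks; the contrast is unbiased; and when the correlations are suitable its interval already allows for chance imbalance on average. ANCOVA against change is partly the analyst's preference. All of that stands, and so does the point that the gain hangs on an unknown rho. With HC3 there is no power gain from about rho 0.8, and with a right-skewed baseline (simulated with all values at least 5%) HC3 coverage was 92.0 to 93.5%, against 93.4 to 95.0% for the difference in mean change. The section also promises to check modelling assumptions, although it names no check of the covariance.

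A reader might infer more than the documents support:
- That the contrast is biased. It is not, over randomisations with complete data.
- That the standard error is right only if all three correlations are equal. It is also about right whenever the two 3-month correlations average to the baseline to 5-week one.
- That adjustment always helps. The plan names a relative 20% decrease but also keeps SD 5.4 afterwards, whereas a pure × 0.8 effect would give 0.8 × 5.4 = 4.32. So the form of the effect is not settled, and under the proportional form the advantage in variance and imbalance is gone by about rho 0.9.
- That the primary outcome should become MRI alone, or that insulin resistance needs a group-by-baseline term because the plan expects that "HIIT will decrease IR especially in those with higher baseline IR". These are separate questions, and this point gives no ground for either change.

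**Conclusion.** The point holds as a modest matter of efficiency and robustness. The planned Aim 1 estimate keeps a (1 - rho) share of a baseline difference whose standard error, 2.10 points, is nearly as large as the 2.3-point target. A one-SE imbalance moves it by 1.05 points at rho 0.5 and 0.21 at 0.9. Adjustment cuts variance by about 23% to 0% over rho 0.5 to 0.95 if the effect is additive. The standard-error issue can be larger (1.90 against 1.33 in one assumed pattern), but its size and direction rest on correlations that the documents do not give.

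The conclusion assumes that the Aim 1 contrast is the group-by-visit interaction, as the between-group wording and hypothesis 1A indicate, and that SDs are equal before and after except where a proportional effect is stated. Between-arm power stays below 70% up to rho 0.9 for the planned contrast and for HC3 ANCOVA; the 8 controls are the larger problem.

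**What to change.** In Data Analysis, base the Aim 1 between-group test on baseline and 5-week data only, adjusted for the baseline value of the same outcome and for sex, the randomisation block. Either an ANCOVA of the 5-week value on group, baseline and sex, or a mixed model with a common baseline mean, would do. Fit the mixed model to two visits or with unstructured covariance. For the ANCOVA report an HC3 standard error, because model-based coverage falls to about 89 to 91% under a proportional effect. Keep the unadjusted difference in mean change as a sensitivity analysis. Fix the choice before outcomes are compared between arms.

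The cost is two or three sentences, no new data and one or two degrees of freedom. Against the planned contrast with equal correlations, HC3 ANCOVA loses 1.5 points of power at rho 0.8 (39.5 - 38.0) and 4.6 at 0.9 (66.9 - 62.3) if the effect is additive. Against the difference in mean change under a proportional effect, it loses about 3 at 0.8 and 6 at 0.9. A two-visit ANCOVA drops anyone without a 5-week value, which matters with 20% dropout expected; the two-visit mixed model with a common baseline mean keeps their baseline data.

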We propose a 4-week HIIT intervention in adolescents (ages 13 to 18, inclusive) with NAFLD. Up to 150 adolescents at-risk for NAFLD will be recruited to be able identify enough number of subjects with NAFLD (prevalence of NAFLD in our cohort was 40%; see data analysis section below). Our goal is to have 46 subjects with NAFLD to complete the study. Subjects will be randomized to either an exercise group or control group at a 5:1 ratio.

Because the objective of the study is to assess the effect of exercise in hepatic steatosis, we will use a multi-step approach to identify subjects with NAFLD and without disqualifiers (see

[figure not shown]

Figure 2. Study Design. FMD, Flow-Mediated Dilation; DXA, Dual X-Ray Absorptiometry; OGTT, Oral Glucose Tolerance Test; MRI, Magnetic Resonance Imaging; ACNC, Arkansas Children’s Nutrition Center; HIIT, High-Intensity Interval Training. *These assessments will only be completed if Visit 5 takes place at ACNC. Note: Physical Activity (PA) assessment via FitBit will also be conducted throughout the study.

exclusion criteria). When available, electronic medical records will be reviewed to identify potential participants. Eligibility will be assessed using a screening form. Potential participants may be screened over the phone or in person. If determined eligible, potential participants will be invited to attend a study visit. Study visits will take place at the Arkansas Children’s Nutrition Center (ACNC) and/or Arkansas Children’s Hospital. Parents and/or participants will be instructed not to come to the study visit and other assessments if parent and/or participant is ill. The visit/assessments will be rescheduled if that is case to a time when parents and participants are well and asymptomatic. **Figure 2** summarizes the study visit schedule for the exercise and control groups as described in detail below.

Participants will be asked not to eat or drink anything (except water) after 10 pm the night prior to the study visits. Due to fasting, study visits will be scheduled in the morning. Study compensation will be provided via ClinCard and/or gift card(s). Lunch and/or snacks may be offered to participants and/or parents at study visits.

Baseline/Pre-Intervention: All Subjects

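### Sex is the randomisation blocking factor but is absent from the analysis model; to the extent that sex predicts change, the Aim 1 test is conservative and its confidence interval too wide

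*Combined protocol and SAP*

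**What the plan says.** Under Study Design and Procedures, the Randomization item of Study Visit 2 states: "We will employ a randomized block design with sex as the blocking factor". Allocation is unequal: "Subjects will be randomized to either an exercise group or control group at a 5:1 ratio". In the Objective/Specific Aims section, Aim 1 assesses the exercise group "compared to a sex-matched control group also with NAFLD with no training".

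The Data Analysis section compares changes between groups "using a linear mixed-effect framework with a subject-level random intercept" and lists the fixed effects in full: "The independent variables will be group (intervention vs control), visit time (baseline, 5-week, 3-month) and their interaction term". It adds: "Changes in the outcomes are defined as difference between follow up visits (5-week and 3-month) versus the baseline". The Aim 1 test is then specified as follows: "Post-hoc contrasts of visit time between 5-week and baseline will be used to test the hypotheses under Aim 1". No other section adds sex to the model, for the primary outcome or for the secondary ones.

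**The concern.** When allocation is balanced within levels of a factor, the between-level part of the outcome variation no longer contributes to the sampling error of the group difference. A model that omits the factor still counts that variation in its residual. The reported standard error then exceeds the true one, the interval over-covers, and the test runs below its nominal level.

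The usual form of this argument concerns a comparison of levels. Aim 1 compares changes, so the part of the variation that matters is the part of the change that differs by sex. With 8 controls planned, the comparison has little precision to give away. The same model also serves fitness, insulin, glucose, adiponectin and the other secondary outcomes. Leaving sex unmentioned also leaves adjustment open to be decided after the data are seen.

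**Working it through.** **Inputs from the documents.** 38 exercise and 8 control completers; baseline IHTG 11.5 with SD 5.4; expected value after training 9.2. The planned effect is 11.5 − 9.2 = 2.3 points, and 2.3/5.4 = 0.426, which agrees with the stated 0.43. The sample-size calculation does not use sex, so the plan has no figure of its own on this point.

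**Assumptions not in the documents.** Two-sided alpha 0.05; equal numbers of each sex in each arm (19/19 and 4/4); SD of the 5-week change 5.4 or 2.7; a sex difference in change, d, of 0, 1.15 (half the planned effect) or 2.3 points (all of it), the same in both arms. Aim 1 is read as the difference between arms in 5-week change, that is, the group-by-visit term.

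**Step 1: would a sex main effect help?** Write each participant's change as follow-up minus baseline. A term that is constant over time drops out of that difference. Random-intercept models fitted to simulated data (38 v 8, 3-month visit in the exercise arm only) confirm this. With complete data, adding sex as a main effect left the Aim 1 estimate unchanged (largest difference below 1e-12), and the ratio of mean standard errors was 1.000, even with a 5.4-point sex difference in IHTG level. With 20% of post-baseline values missing at random, the ratio was 0.997 to 1.000, although in a single data set the estimate could move by up to about 1 point.

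**Step 2: what does omitting sex-by-visit cost?** With equal sexes, the share of the variance of change due to sex is

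R² = (d/2)² / SD²,

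and the interval without sex is wider than the interval with sex by a factor of about 1/√(1 − R²).

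- SD 5.4, d = 1.15: R² = 0.575²/5.4² = 0.331/29.16 = 0.011; factor 1.006.
- SD 5.4, d = 2.3: R² = 1.15²/5.4² = 1.3225/29.16 = 0.045; factor 1.023.
- SD 2.7, d = 1.15: R² = 0.331/7.29 = 0.045; factor 1.023.
- SD 2.7, d = 2.3: R² = 1.3225/7.29 = 0.181; factor 1.105.

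Simulating the 5-week change regressed on group, with and without sex (200,000 trials per setting), which also accounts for the degrees of freedom, gave:

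| SD of change | Sex difference in change | Unadjusted CI wider by | Type I error, unadjusted | Power, unadjusted → adjusted |
|---|---|---|---|---|
| 5.4 | 0 | 0% | 5.0% | 19% → 19% |
| 5.4 | 1.15 | about 0.5% | 4.8% | 18.6% → 18.9% |
| 5.4 | 2.3 | about 2% | 4.5% | 18% → 20% |
| 2.7 | 0 | 0% | 5.0% | 57% → 57% |
| 2.7 | 1.15 | about 2% | 4.5% | 57% → 59% |
| 2.7 | 2.3 | about 11% | 3.1% | 58% → 66% |

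With sex in the model, type I error was 4.9% to 5.1% in every row. With exact balance the point estimate is the same with and without sex; only the standard error changes.

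**Step 3: does this carry over to the three-visit model?** In the fitted random-intercept model with a 2.3-point sex difference in change, the standard error of the Aim 1 contrast was 1.656 without sex and 1.613 with sex and sex-by-visit. That is 1.656/1.613 = 1.027, or about 3% wider. With 20% of post-baseline values missing it was 1.8675/1.8225 = 1.025. The gain is of the same order as in Step 2.

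**The case against.** The strongest objection is that the loss is conditional and the plan is valid as written. No passage says that sex predicts the change in IHTG, the pilot table gives no figures by sex, and the Aim 1 hypotheses name no sex difference. If there is none, omitting sex costs nothing. All of this stands, and the point is limited accordingly.

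A reader might infer that the Aim 1 standard error is simply too large because a blocking factor was left out. The documents do not support that. It would follow for a comparison of IHTG levels, but Aim 1 uses change from own baseline, and the effect of sex on change is unknown.

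A reader might also suppose that sex explains 10%, 20% or 30% of the variance of change, which would widen the interval by about 5%, 12% or 20%. With equal sexes and SD 5.4, those shares mean sex differences in 5-week change of 2 × 5.4 × √0.10 = 3.4, 2 × 5.4 × √0.20 = 4.8 and 2 × 5.4 × √0.30 = 5.9 points, in untrained controls as well. The planned training effect is 2.3 points. Nothing in the documents supports sex effects of that size.

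Finally, the sex term is minor beside the shortage of controls. That is right: at SD 5.4, two-sided between-group power is about 19% with or without it. It does not argue against a nearly free change. With no sex effect on change, adjustment cost nothing measurable in the simulations; with one, it restored the nominal level and gained some power.

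**Conclusion.** The omission is certain: sex is built into the randomisation and missing from the model. The consequence is conditional and probably small for IHTG. The loss is within the ranges tabulated above if the sex difference in change is no larger than the planned training effect. It reaches about 11% of interval width only if that difference equals the whole planned effect and the SD of change is half the baseline SD. These figures rest on assumed sex differences, an assumed SD of change, equal sexes and exact balance within arm. For the secondary outcomes no size can be given, because the documents provide no sex-specific data and only IHTG was calculated.

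This is a worthwhile refinement that aligns the analysis with the design and fixes the choice in advance. It does not put the validity of the trial in question.

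**What to change.** In the Data Analysis section, add sex and sex-by-visit as fixed effects to the model for IHTG and for each secondary outcome. An equivalent form for Aim 1 is sex as a covariate in a model of the 5-week change. Both terms are needed, for the reason given in Step 1. Keep the difference between exercise and control in 5-week change as the Aim 1 estimate.

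The cost is one sentence. Sex is already recorded for the blocking, and the model loses one or two degrees of freedom; in the 5-week change model they go from 44 to 43. The shortage of controls needs to be addressed separately.
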